# SUMMARY

Title of the study	Nutritional Intake of "Finger-food" on Elderly People in Seniors's					
Title of the study	Resident (FIFO)					
Keys words	« Finger food », nutrition					
Head of research	Centre Hospitalier Départemental de Vendée – La Roche sur Yon					
Number of centers planned	Monocentric study carried out on elderly people in senior's resident of the CHD VENDEE. - Site de LRSY : Le Marais / La Plaine Principal Investigator : Mme [name] - Site de Luçon : La Roseraie Principal Investigator : Mme [name] L'Olivier (seniors's residents) Principal Investigator : Mme [name] - Site de Montaigu : Augereau Principal Investigator : [name] Soleil de la Maine Principal Investigator : [name]					
Type of study	Research evaluating routine care					
Planning of the study	Total duration: 8 months Recruitment period: 1 month Duration of follow-up per resident: 7 months					
Study design	
 
Nursing study
 
Study pilot
 
Monocentric
 
Prospective
 
Randomized in 2 parallel groups         
 
Arms without finger-food
 
Arms with finger-food
 
Open
 
 
 
					
Objectives of the study	
 
Main objective : To evaluate the added value of "finger-food" on the nutritional intake on elderly people in seniors's resident
 
Secondary objective(s) : 
 
Describe the evolution :
 
Nutritional status
 
Associated comorbidities
 
From autonomy
 
Behavior around the meal
 
Resident satisfaction / pleasure of eating
 
The burden of hotel/care on elderly people in seniors's resident
 
 
 
					
Projected number of cases	All elderly people in seniors's resident who met the inclusion criteria at the beginning of the study will be included. Of the 269 residents institutionalized in these facilities, we estimate that about 60 subjects meet all the criteria.					

	
 
Recruitment period: 1 month
 
Duration of follow-up per resident: 7 months
 
					
	• Duration of follow-up per resident: 7 months					
	Collect of :					
	
 
Nutritional intake
 
Nutritional indicators
 
					
Schedule of the different	- Associated comorbidities					
visits and examinations	- Associated comorbidities - Autonomy					
	- Behavior					
	- Satisfaction / pleasure of eating					
	- Impacts on serniors's resident professionals					
	- Significant events on food intake					
	Inclusion criteria :					
	- Residents institutionalized in seniors's resident for 3 months					
	at least Decidents in dischility to food single handedly because of					
	
 
Residents in disability to feed single-handedly because of cognitive and/or physical disorders
 
					
	- Having at least use of a hand					
	- Do not opposing the participation in the study or information					
	and not opposition of the family / close to confidence / legal					
Criteria	guardian in case of resident in incapacity to understand					
	(senility, insanity)					
	Exclusion criteria :					
	- Confined to bed					
	
 
Specific diets (without residue, allergen,)
 
Enteral nutrition
 
					
	
 
Absence motricity of 2 hands
 
					
	Quantitative measurement of ingesta (caloric and protein intake),					
Primary endpoint	monthly between M-1 (before implementation of the "finger-food")					
	and M6.					
	Nutritional indicators:					
	Weight curve BMI					
	Biological indicators: Albumin / Pre-albumin, CRP					
	MNA Score Screening					
	Associated Comorbidities:					
	Number of wounds and pressure sores					
	Number of falls					
Secondary endpoint(s)	Autonomy					
	Autonomy : Power supply autonomy: EBS					
	Physical or psychological autonomy: GIR					
	Behavior around the meal:					
	- Assessment of eating disorders: Blandford scale					
	Resident satisfaction / enjoyment of food: VAS					
	Hospitality/care load of seniors's resident professionals					

Expected results	
 
This study will evaluate each of the defined evaluation criteria, analyze them in order to measure their impact on the following criteria: 
 
Maintain and/or improve the nutritional status of residents
 
Improvement of autonomy, behavior, quality of life
 
Reduction of associated comorbidities
 
 
 
Then to think about other projects, by formalising hypotheses, with an impact study.
 

------------------	--

# 1. JUSTIFICATION OF THE STUDY

Undernutrition and the prevention of its risk in elderly people in seniors's resident constitute a major public health issue. The diagnosis of undernutrition and its risk are systematically recommended in these structures where the food of the persons is a problem because often unsuited to their capacities of grip and consequently to their nutritional needs. One of the solutions to remedy this could be the food offer proposed by the "finger-food".

The FIFO (Finger-Food) study, with a monocentric and randomized design, aims to verify the hypothesis that "finger-food" would increase food intake in seniors's residents with prehension disorders and/or requiring feeding stimulation and/or assistance with meal preparation.

### **1.1 GENERAL DESCRIPTION OF THE STUDY**

The scientific justification of this study project is organized in two parts. The first part deals with the aging population in France, with a snapshot of the epidemiology, undernutrition (definition, causes, consequences), its link with aging and loss of autonomy. The nutritional strategies that can be used to prevent or treat undernutrition are then presented. The "fingerfood" is one of them. After a presentation of this concept, we will highlight the current problem of the lack of proof of its effectiveness, which this study aims to fill.

The second part of this justification will focus on the Vendée department, the population in which this study will be carried out, and more specifically within the seniors's resident of the Centre

Hospitalier Départemental (CHD) of Vendée. Finally, the main objective of the study will be formalized and supported by secondary objectives, which will be developed in the relevant paragraph.

The increase in life expectancy is leading to an aging population in France. Indeed, while there are currently 15 million people over the age of 60, the project on the adaptation of society to ageing carried out by Marisol TOURAINE1 and Pascal BOITARD2, clearly sets the context by estimating that there will be 20 million of them in 2030 and nearly 24 million in 2060. The over 75s represented 5.7 million in 2012, they will be 12 million in 2060. As for the over 85s, their number will increase from 1.4 million to 4.8 million in 2050 [1].

As a consequence of this aging process, the institutionalization of elderly people with a loss of autonomy is on the rise in France. This loss of autonomy impacts the quality of life of seniors's residents, their nutritional status and can progressively lead to a rupture of social ties.

As Claude FISCHLER [2] points out, "eating: nothing more vital, nothing more intimate"; eating is not only a vital physiological need but also an emotional and relational act. For residents who are unable to feed themselves, the psychological impact is strong and leads to a loss of confidence and self-esteem. Meals are no longer experienced as a moment of pleasure but of stress. The assistance of the caregivers in feeding, by giving food with a spoon, can sometimes be invasive and give the image of dependence. The meal, very badly lived, then becomes an anguishing moment, of shame and embarrassment for the residents.

A prospective survey carried out in 67 French seniors's residents on the nutritional status of 1550 residents highlighted the need for assistance with meals for 31% of the subjects [3]. Many of them progressively lose their appetite, with the onset or even worsening of undernutrition, a real public health problem in seniors's residents. A 2011 French study [4], involving 57 seniors's residents and 4520 residents with an average age of 85.8 ± 7.8 years, showed that 45.6% (44.2% - 47.1%) of the residents had undernutrition, including 12.5% with severe undernutrition. In addition, dependence on food was the characteristic that most discriminated between undernourished residents and others (+23.9%). According to P. BROCKER3 , the prevalence of undernutrition in institutions varies between 15 and 38% [5]. M. FERRY4 estimates that the prevalence of undernutrition can reach 70% of elderly patients in hospitals [6].

According to the Agence Nationale d'Accréditation et d'Evaluation en Santé (ANAES), protein-energy undernutrition results from an imbalance between the body's protein-energy intakes and needs [7]. The Haute Autorité de Santé (HAS) [8] defines the diagnosis of undernutrition according to the existence of one or more of the following criteria: weight loss  $\geq 5\%$  in 1 month and/or  $\geq 10\%$  in 6 months and/or Body Mass Index5 (BMI) < 21 and/or Albuminemia < 35g/I (to be interpreted taking into account the C-reactive Protein (CRP)) and/or overall Mini Nutritional Assessment6 (MNA) < 17. Undernutrition is characterized as severe if weight loss  $\geq 10\%$  in 1 month and/or  $\geq 15\%$  in 6 months and/or BMI < 18 and/or Albumin < 30g/I.

Undernutrition leads residents into a vicious circle, as described by M. FERRY [9]; a vicious circle that is self-perpetuating between the causes and consequences of undernutrition. The risks of comorbidities and mortality increase [10], with an increased risk of bedsores and falls.

A study carried out on 8428 hospitalized patients, on the relationship between mortality and

BMI, shows a mortality three times higher in subjects aged 70 to 79 years, when the BMI was lower than 18, compared to a BMI between 32 and 40 [11].

In addition, the quality of life of the residents is altered [12] and they become more prone to develop swallowing disorders, food dependency, hunger sensation disorders and modified texture sometimes becomes necessary.

In spite of the respect of nutritional needs, today, the food offered to these patients is rarely effective because it is not very appetizing, always presented in the same way and consequently little consumed [13]. The notion of pleasure is no longer present. Also, as specified by A.RAYNAUD-SIMON7, "in institutions, the prevalence of undernutrition is linked to the importance of pathologies and dependence, but also to the quality of the food service and the time available to caregivers to help with feeding" [6].

In order to fight against this public health problem, the National Nutrition and Health Program

(PNNS) 3 (2011-2015) [14] has defined, through axis 3, actions to reduce the prevalence of undernutrition. In this respect, a certain number of nutritional strategies can be implemented, such as oral nutritional supplements, "homemade" enriched preparations, dietary advice, pleasure trays" or even "finger-food". Developed in seniors' for about ten years, the "finger-food" approach is not new. It has been implemented in order to meet the specific needs of residents, but without measuring its impact. This concept of "finger-food", also called "finger-food", has been particularly developed by Pr Charles Henri RAPIN8, in a geriatric unit in the Canton of Geneva (Switzerland) and consists in proposing dishes that can be seized with the fingers and eaten as such. Most often, these are individual bites with a high energy density in a small volume. The objective is to stimulate the appetite and the autonomy of people who need it [15].

There has been little research on this concept. A 2015 review of the practicalities of "fingerfood" confirms the "lack of hard evidence of its effectiveness in the scientific literature" [16].

The Nancy University Hospital has evaluated the impact of "finger-food" on the food intake of demented patients [17]. This evaluation showed a significant increase in protein intake, but it seems to be effective only in certain patients (those with the least associated pathologies and who have retained the ability to eat).

The hospital of Gimont (32) has questioned this concept of "finger-food" which would seem to maintain and/or give back autonomy to the residents, thanks to easy finger foods [18]. It would also tend to guarantee the residents sufficient nutritional intake (caloric and protein) to cover their needs, which are often increased due to the high prevalence of undernutrition or its risk in seniors's residents.

In addition, this concept could reduce food waste, which is important in seniors's residents,

due to a service that is not always adapted to the expectations and needs of residents [19]. In this national context, according to the National Institute of Statistics and Economic Studies

(INSEE), "the Vendée could see the number of people aged 60 or more double between 2007 and 2040, to reach 310,000 inhabitants: seniors would then represent 36% of the Vendée population" [20]. Moreover, the number of people over 80 years old will increase by 57,000 between 2010 and 2040. The department of Vendée will thus experience, along with Loire-Atlantique, the most significant aging in the Pays de la Loire region [21].

An Evaluation of Professional Practices (EPP) relating to undernutrition carried out at the CHD Vendée highlights a significant prevalence of undernutrition or its risk, regardless of the medical and surgical sectors, and concerns 30 to 50% of patients (source: data communicated by the Dietetics and Nutrition Unit of the CHD Vendée).

As the proportion of elderly people is high in these sectors, the prevalence of undernutrition in seniors's residents can be estimated at one in three or even one in two patients. A survey conducted by the CHD Vendée catering service showed that 30% of long-stay patients have a modified texture diet. In addition, 20% of meals in the Long-Term Care Unit (USLD) are not consumed (source: data provided by the CHD Vendée catering service). To remedy this problem, the CHD catering service has received theoretical and practical training for a new presentation of modified textures. The tests carried out with the patients following this training were well perceived with 3 positive points noted: increase in the quantities eaten, increase in the time spent at the table, socialization of the patients. This multidisciplinary research project proposed at the CHD Vendée is part of a desire to consider food as a care in its own right and supports the institutional work of individualizing the care of the resident, via the personalized life project developed for each of them within these structures.

The main objective of this study is to evaluate the added value of "finger-food" on the nutritional intake of seniors's residents who are unable to eat with cutlery and/or who require stimulation of food intake and/or assistance with meal preparation.

As weight, BMI and albumin levels are subject to multifactorial variations, the main objective of this study will be to target the dietary intakes of these patients and more precisely, the caloric and protein intakes. The other evaluation criteria of the nutritional status specified above will be evaluated as secondary objectives, as will be the impact of eating hands on falls, pressure sores, quality of life, autonomy of eating, behavior around meals, pleasure of eating or the care load of professionals. These criteria will be further documented in the "secondary objectives" section.

The willingness of the CHD management to maintain this "finger-food" service beyond the study for residents who wish and/or need it, is a real opportunity to respond to the essential values of pleasure, conviviality, self-esteem and freedom of choice, as well as to the needs

of the residents, notably autonomy and nutritional status. The act of eating, beyond its primary function of feeding, must remain a source of pleasure. As J-A BRILLAT-SAVARIN [22], a French gastronome, stated, " the pleasure of the table is for all ages, all conditions, all countries and all days; it can be associated with all pleasures and remains the last to console us for their loss ".

# **1.2** SUMMARY OF BENEFITS, IF ANY, AND FORESEEABLE AND KNOW RISKS TO INDIVIDUALS INVOLVED IN THE STUDY

There are no foreseeable risks associated with participation in the study. Residents will be managed according to standard practice.

In contrast, this study seeks to demonstrate the predictable direct benefits to the residents participating in the study:

- Maintain or improve nutritional status
- Improved autonomy, behavior, and quality of life
- Reduction of associated comorbidities

# **1.3 STATEMENT THAT THE STUDY WILL BE CONDUCTED IN ACCORDANCE** WITH THE PROTOCOL AND WITH GOOD CLINICAL PRACTICE AND THE LEGISLATIVE AND REGULATORY PROVISIONS IN FORCE

The investigator also agrees that this study will be conducted:

- in accordance with the protocol,
- in accordance with the recommendations of the "Declaration of Helsinki
- in accordance with current French and international Good Clinical Practices
- in accordance with the laws and regulations currently in force in France and internationally

The investigator undertakes to comply with all legislative and regulatory provisions that may apply to the study.

# 2. OBJECTIVE AND ENPOINTS

### 2.1 PRIMARY OBJECTIVE AND ENDPOINT

### 2.1.2 Primary objective

To evaluate the added value of "finger-food" on the nutritional intake of residents in seniors's residents.

### 2.1.3 Primary endpoint

Quantitative measurement of ingesta (caloric and protein intake), monthly between M-1 (before implementation of the "finger-food") and M6.

The assessment of nutritional intakes will be carried out on 3 consecutive days, by a dietician, for lunch and dinner, at a point in time between M-1 and M0 (i.e. before the implementation of the "eat-in" system), and then monthly.

This dietary assessment will be done by means of photos BEFORE/ AFTER the consumption of the meal, by the housekeepers. The photos will target the actual consumption of the meal compared to the proposed service. This tool is preferred to the food monitoring form, usually used in the seniors's residents, but which does not allow for a detailed analysis of the food consumed and the quantities per dish actually ingested by the residents.

Also, the environment of the meal will be photographed in order not to wrongly consider the possible food losses, notably food on the ground, as food contributions. The residents' faces will not be photographed.

Information on the taking of these photographs will be provided to the appropriate people in order to have an image quality that is conducive to analysis and to respect a certain homogeneity of distance in the taking of photographs and in the analysis that will result from them.

The same dietician will ensure the analysis of the photos and intakes to avoid bias.

The photos will be analyzed using a quantitative and qualitative approach:

Meal consumption: A global evaluation of the meal will be done according to whether the resident ate all of his meal, /4, half, /4 of his meal or nothing at all, while taking

into account the environment.

- Type of dish consumed (starter / main course: meat-fish-egg, vegetable-starch / dairy product / dessert).
- The caloric (in kilocalories) and protein (in grams) intakes of the meal trays will be calculated before distribution to the residents.
- The same calculations will be made after the meal has been consumed, taking into account the environment and what the resident has actually eaten. They will be compared to the amount of the proposed meal tray in order to take into account residents with a poor appetite for whom half portions are usually proposed.

### 2.2 SECONDARY OBJECTIVES AND ENDPOINTS

### 2.2.1 Secondary objectives

Describe the evolution:

- Nutrional status
- Associated comorbidities
- From autonomy
- Behavior around the meal
- Resident satisfaction/ pleasure of eating
- The burden of hospitality/ care for seniors's residents professionals

#### 2.2.2 Secondary endpoints

All endpoints will be compared between the no "finger-food" period (M-1 - M0) and the resident follow-up period (M0 to M6) depending on the randomization arm.

#### Nutritional indicators :

- Monthly weight

The same scale will be systematically used on each seniors's residents.

- Monthly BMI

Please note: a height measurement will be taken at inclusion

\_

Biological indicators (albumin / pre-albumin, CRP) at M-1 and M6

The albumin/pre-albumin and CRP blood tests will be taken into account only in the absence of an inflammatory syndrome. In case of CRP > 15 (HAS recommendations - 2003) [23], it will not be taken into account in the analysis.

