### 5.2 STUDY SCHEDULE

Actions		Inclusion	M-1 to M0	M0 to M1	M1 to M2	M2 to M3	M3 to M4	M4 to M5	M5 to M6
Collection of non-opposition Size measurement		X							
Randomization			х						
Collection of consumption: nutritional intake*.			х	х	х	x	х	х	x
Nutritional Indicators**			x	x	Х	Х	х	x	х
Nutritional Indicators***			Х						х
Associated comorbidities ****			Х	Х	Х	Х	Х	Х	Х
Autonomy	Power supply (EBS)		Х			Х			Х
Autonomy	GIR		Х						Х
Eating behavior (Blandford scale)			Х			x			х
Resident satisfaction (VAS of faces)			Х	Х	Х	X	Х	Х	x
Impact on professionnals			Х	Х	Х	X	Х	Х	x
Significant events on food intake *****			Х	Х	Х	Х	Х	Х	Х

\*3 consecutive days, for lunch and dinner, at a time t between M-1 and M0, then monthly

\*\*Weight, BMI \*\*\* Biological indicators (albumin/ pre-albumine/ CRP), MNA screening score \*\*\*\* Number of pressure score and severity, number of falls, infectious complications: over the entire study period \*\*\*\*\* Medical and environmental events, drug consumption, hospitalization (number, reasons, duration)

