#### Nutritional indicators :

The evolution of all nutritional indicators between inclusion and 6 months will be compared between the 2 groups by a Wilcoxon Mann-Whitney test.

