# 10. RATIONALE FOR REQUESTING VALIDATION OF CURRENT CARE STUDY

Based on all of these elements, the principal investigator qualifies this research as primarily **routine care research**, since:

- All procedures are performed as usual (biological samples for assessment, clinical data).

The study does not focus on techniques or strategies that are neither innovative nor obsolete. Blood samples will be taken as described in the usual check-ups.

An additional assay (albumin/pre-albumin/CRP) will be performed.

This assay involves a blood test to be performed outside of standard practice (albumin/prealbumin and CRP assay: once a year as part of standard practice). It will also be coupled, whenever possible, with another blood test.

Apart from this dosage, the overall care of the resident will be identical to the usual practice.

Consequently, the particular modalities of implementation in the research represent negligible constraints for the person who lends himself to the research. (Article R 1121-3 of the public health code (CSP), decree n° 2006-477 of 26 April 2006).

The person in charge of the research will therefore, before any implementation of the research, submit the study protocol to the Comité de Protection des Personnes Ouest V de Rennes for a favourable opinion and confirmation of the qualification of the research, accordance with article L 1121-1 of the public health code (CSP) as they result from the laws n°2004-806 of August 9, 2004 and n° 2006-450 of April 18, 2006 relating to the public health policy.

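### CRP is a compared secondary endpoint, yet the inflammation rule (CRP > 15) as worded removes high CRP values from its own comparison

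*Combined protocol and SAP*

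**What the plan says.** CRP appears among the secondary endpoints in three places. The Summary has "Biological indicators: Albumin / Pre-albumin, CRP". Section 2.2.2, under the nutritional indicators, has "Biological indicators (albumin / pre-albumin, CRP) at M-1 and M6". The footnote to the schedule in section 5.2 has "Biological indicators (albumin/ pre-albumine/ CRP), MNA screening score".

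Section 6.2.1 makes no exception for CRP: "The evolution of all nutritional indicators between inclusion and 6 months will be compared between the 2 groups by a Wilcoxon Mann-Whitney test".

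The rule at issue is in section 2.2.2 and has two sentences. The first is "The albumin/pre-albumin and CRP blood tests will be taken into account only in the absence of an inflammatory syndrome". The second is "In case of CRP > 15 (HAS recommendations - 2003) [23], it will not be taken into account in the analysis". Neither names a visit, and the threshold carries no unit.

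Section 1.1 gives the apparent reason in its list of criteria for undernutrition: "Albuminemia < 35g/I (to be interpreted taking into account the C-reactive Protein (CRP". Section 6.2.7 has all included residents analysed. The missing-data rule in section 6.2.5 is framed around intake, so it does not cover laboratory values that this rule removes.

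**The concern.** A variable that is itself an outcome should not be filtered on its own value. If high CRP results are dropped, the comparison covers only residents whose CRP stayed low, and the large movements, which carry most of the information about inflammation, are lost.

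The wording also leaves the statistician unsure what to do. In the second sentence, 'it' could mean the CRP result, the albumin and pre-albumin results, or the whole panel. If it means albumin and pre-albumin only, it does not match the first sentence, which names the CRP test. If it includes CRP, the CRP comparison loses its upper end. The text also does not say whether one high visit removes that value or the whole change score.

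Timing is a separate matter. Section 5.1, step 1, places the initial assessment before randomisation, so M-1 is a baseline value and M6 a post-randomisation one. Because no visit is named, the rule appears to apply at M6 as well, where it selects residents on something measured after allocation.

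**Working it through.** The documents contain no CRP figure to reproduce, and section 6.2.2 states that no sample size calculation was made. The check is therefore a reading of the text, one bound, and illustrations under assumed inputs.

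**Inputs from the documents.** About 60 residents (section 4.1); 1:1 allocation (section 3.3), hence about 30 per arm; tests at M-1 and M6; cut at 15; Wilcoxon Mann-Whitney test on the change; 5% level (section 6.2.3).

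**Bound.** This rests on three readings: the rule covers CRP, it acts at both visits, and a dropped value removes the pair. Then 0 < CRP(M-1) ≤ 15 and 0 < CRP(M6) ≤ 15, so −15 < change < +15. A rise from 6 to 14 counts as +8; a rise from 6 to 60 (+54) does not count.

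**Pairs retained (illustration).** Let p be the assumed share above 15 at each visit. Pairs = 60 × P(both visits ≤ 15). Independent visits give 60(1−p)²; complete overlap gives 60(1−p), which is also what a rule at M-1 only would keep. The middle column uses a bivariate normal model for log CRP.

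| p | independent | correlation 0.5 | complete overlap, or M-1 rule only |
|---|---|---|---|
| 10% | 49 | 50 | 54 |
| 20% | 38 | 41 | 48 |
| 30% | 29 | 33 | 42 |

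**Shrinkage at M6 (illustration).** Log CRP is taken as normal with mean μ = ln(median) and SD σ, and cut at ln 15. The mean after the cut is μ − σφ(b)/Φ(b), with b = (ln 15 − μ)/σ. With median 5 or 8 and σ 1.0 or 1.2, taking the stated median as the lower and then as the higher arm, a true 1.5-fold ratio of geometric means appears as 1.20 to 1.34, and a 2-fold ratio as 1.34 to 1.69. These ratios describe the M6 values with the cut at M6 only, not the change that section 6.2.1 tests.

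**Power for the change (illustration).** Simulation with 30 v 30 residents, log-normal CRP, correlation 0.5 between visits, a 2-fold arm effect at M6 only, the filter at both visits, and a two-sided Wilcoxon Mann-Whitney test at 5% on the raw change.

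| Median / σ | one arm falls: all values → filtered | one arm rises: all values → filtered |
|---|---|---|
| 5 / 1.0 | 54 → 44% | 73 → 41% |
| 5 / 1.2 | 40 → 29% | 55 → 27% |
| 8 / 1.0 | 53 → 34% | 72 → 26% |
| 8 / 1.2 | 39 → 23% | 56 → 18% |

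With no arm effect, rejection is about 4 to 5% with or without the filter. With a 2-fold rise the arms keep unequal numbers out of 30: 23 v 18 (5 / 1.0) to 17 v 12 (8 / 1.2).

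**Albumin (illustration).** Assume albumin is 2 g/L lower per log-unit of CRP, with residual SD 3 g/L and residual correlation 0.6. A direct 2 g/L arm effect with no effect on CRP is recovered without bias (1.99 to 2.03). Only precision is lost: power goes from 60 to 52%, 55 to 45%, 60 to 43% and 54 to 35% in the four settings above. If the arm acts on albumin only through a 1.5-fold change in CRP, the true difference is 2 × ln 1.5 = 0.81 g/L. The filtered comparison shows about 0.59 to 0.68 when CRP falls and 0.53 to 0.62 when it rises.

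**The case against.** The strongest reply is that CRP was never meant as an outcome. Section 1.1 brings CRP in only to help interpret albumin, and its statement of the nutritional markers subject to multifactorial variation names weight, BMI and albumin but not CRP. No hypothesis that finger-food changes CRP is stated. On this reading CRP is a validity check and the wording is loose. That is plausible, and the fix allows for it. It does not settle the matter, because the Summary, section 2.2.2 and section 5.2 all list CRP as an indicator and section 6.2.1 compares every indicator.

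Three stronger inferences are tempting, and the documents do not support them.

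- *That the bound of 15 follows from the text alone.* It needs the three readings set out in the working. Application at M6 is inferred from the lack of a visit limit.
- *That the albumin comparison is biased.* The rule has a measurement rationale there, and bias arises only if the arm affects CRP. The protocol hopes for fewer comorbidities, but nowhere says that CRP will move.
- *That blood taken for the study is wasted.* Section 10 does say "This assay involves a blood test to be performed outside of standard practice", but it also plans to combine it with another sample where possible, and a CRP above 15 still decides whether albumin can be interpreted.

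It is also fair to say that every retention, ratio and power figure rests on inputs that are not in the documents.

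**Conclusion.** The point holds for CRP. Taken at its word, section 2.2.2 truncates a compared endpoint on its own value, and no other section corrects this. The consequence is an understated arm difference and lower power, not a false-positive risk. Under the three readings, changes of 15 or more cannot enter; beyond that, the size cannot be derived from the documents.

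If 'it' is confined to albumin and pre-albumin, the truncation goes away, but the two sentences then disagree and still need repair. For albumin and pre-albumin the restriction is defensible. Used at M6 it costs residents, and it biases the comparison only if the arm changes CRP.

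Priority is low. Only secondary laboratory comparisons of a pilot are affected, and the primary endpoint is untouched.

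**What to change.** In sections 2.2.2 and 6.2.1:

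1. Replace 'it' with the named tests. Limit the CRP > 15 filter to albumin and pre-albumin, state the visits at which it applies, and compare all measured CRP values with the planned Wilcoxon Mann-Whitney test. Alternatively, if CRP is meant only as a validity check for albumin, say so and remove it from the compared endpoints.
2. Report the number of residents with CRP > 15 by arm and visit.

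Optional: show albumin and pre-albumin with all measured values as a sensitivity analysis beside the planned restricted analysis.

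The cost is a text change and one count table, with no new samples and no change of test. If the optional analysis is used, the two albumin results may differ and will need a sentence of interpretation, since albumin from inflamed residents is a noisier marker of nutrition.
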